### **Abbreviations**

Abbreviation	Explanation
ACR ®	American College of Radiology
BI-RADS ®	Breast Imaging Reporting and Data System
СС	Cranio-Caudal
CFR	Code of Federal Regulations
CRF	Case Report Form
DBT	Digital Breast Tomosynthesis
DCF	Data Clarification Form
DMC	Data Management Center
DVIIm	Dynamic Visualization for Mammography
EDR	Exposure Data Recognizer
EDR2m	Exposure Data Recognizer 2 for Mammography
FBP	Filtered Back Projection
FDA	Food and Drug Administration
FFDM	Full-Field Digital Mammography (also known as Digital Mammography)
GCP	Good Clinical Practice
HIPAA	Health Insurance Portability and Accountability Act
ICH	International Conference on Harmonization
ID	Identification
IRB	Institutional Review Board
ISR	Iterative Super-Resolution Reconstruction
LCC	Left Cranio-Caudal
LMLO	Left Medio-Lateral Oblique
MFP	Multi-Objective Frequency Processing
MFP2	Multi-Objective Frequency Processing 2
MLO	Medio-Lateral Oblique
MQSA	Mammography Quality Standards Act

PHI	Protected Health Information
PMA	Premarketing Approval Application
RCC	Right Cranio-Caudal
RMLO	Right Medio-Lateral Oblique

Page 6 of 31

### **Definitions**

	Ţ
ACR® BI-RADS®	a. The breasts are almost entirely fatty
Breast Tissue	b. There are scattered areas of fibroglandular density
Composition	c. The breasts are heterogeneously dense, which may obscure small masses
(Density) Categories	d. The breasts are extremely dense, which lowers the sensitivity of mammography
	Assigned by reader; 0 = Incomplete - Need Additional Imaging Evaluation and/or Prior Mammograms for Comparison
	1 = Negative
	2 = Benign
ACR ® BI-RADS ® Assessment Categories	3 = Probably Benign. Management: Short-interval (6-month) follow-up or continued surveillance mammography
Categories	4 = Suspicious. Management: Tissue diagnosis.
	4A = Low suspicion for malignancy
	4B = Moderate suspicion for malignancy
	4C = High suspicion for malignancy
	5 = Highly Suggestive of Malignancy
ASPIRE Bellus II	Fujifilm mammography viewer (see Appendix A) where the FFDM and DBT images are displayed and reviewed by the physician.
ASPIRE Cristalle with DBT Option	Fujifilm's Mammography Acquisition System (see Appendix A) which generates both FFDM and DBT images.
Benign Case	A case in which all lesions are confirmed as benign by a biopsy or surgery and no other lesions are biopsy-malignant.
Cancer Case	A case in which at least one lesion is confirmed as malignant by biopsy or surgery.
Case	Two views (CC and MLO) of one breast.
	Each DBT Examination has two parts:
DBT Examination	
 
Acquisition: Acquisition of DBT images for each of the standard bilateral CC and MLO views (RCC, LCC, RMLO, LMLO) using the ASPIRE Cristalle.
 
Review: DBT images are displayed and interpreted by the physician on the ASPIRE
 

	Bellus II.
DBT Images	A series of mammograms, which are reconstructed from multiple low-dose projection images captured by the ASPIRE Cristalle with the x-ray tube rotated at a number of small offset angles over a limited angular range while the breast remains compressed and unmoved.
DBT Read	The physician reads (interprets) the DBT images displayed on the ASPIRE Bellus II (see Appendix A)
DBT Views	A series of cross-sectional views of the DBT images for each of the CC and MLO views for each breast.

Evaluable Subject	Based on acquisition-site data, an evaluable subject is a subject with known true clinical status and with complete DBT and FFDM examinations (four standard views), in which there is sufficient anatomical coverage, sufficient contrast, no significant motion or other artifacts, limited noise, and similar positioning.
FMSU2013-004A	Acquisition of Digital Mammography and Breast Tomosynthesis Images for Clinical Evaluation of Fujifilm Digital Breast Tomosynthesis
FMSU2017-003	A Feature Comparison Study to Evaluate the Modified Processing of Fujifilm's ASPIRE Cristalle with Digital Breast Tomosynthesis Option as Compared to the Original Processing
Fujifilm	FUJIFILM Medical Systems, U.S.A., Inc.
IA Site DBT Reader	An image-acquisition site reader is an MQSA-qualified radiologist who interprets the DBT images at the time of image acquisition (see FMSU2013-004A).
Image Set	One (1) image with Original Processing, and one (1) image with Modified Processing of two views (CC and MLO) of the same breast.
Modified Processing	Fujifilm's ASPIRE Cristalle with Digital Breast Tomosynthesis Option with a) iterative super-resolution reconstruction (ISR) and b) Dynamic Visualization II for Mammography (DVIIm = EDR2m + MFP2) presentation processing.
Negative Case	A negative case is defined as a case where there are no abnormal areas or malignant (cancer) findings within a year (within 320 to 455 days) from the original screening examination.
Non-Cancer Case	A biopsy benign case, or a recall case, or a normal case.
Original Processing	Fujifilm's ASPIRE Cristalle with Digital Breast Tomosynthesis Option with FDA-approved filtered back projection (FBP) with EDR and MFP presentation processing.
Prior Mammogram	Historical mammogram acquired on any media – including screen-film, digitized image, FFDM and/or DBT.
Recall Case	A case where there is a suspicious area(s) identified in the screening exam that needs additional work-up to determine if the area is cancerous or not. This is determined at the IA site.
Standard views	Standard CC and MLO views for each breast (RCC, LCC, RMLO, LMLO).

# 3. Protocol Synopsis

SPONSOR NAME	FUJIFILM Medical Systems U.S.A., Inc.
PROTOCOL NUMBER	FMSU2017-003
STUDY TITLE	A Feature Comparison Study to Evaluate the Modified Processing of Fujifilm's ASPIRE Cristalle with Digital Breast Tomosynthesis Option as Compared to the Original Processing
DEVICE NAME	Fujifilm ASPIRE Cristalle with DBT Option Utilizing ISR and DVIIm
PURPOSE	The purpose of the feature comparison study is to evaluate general mammographic features in images of the same breast when reconstructed with modified (ISR and DVIIm) processing as compared to the original processing (FBP with EDR and MFP).
	One breast per subject (two views per breast) will be assessed by approximately six (6) readers.
STUDY OBJECTIVES	The following primary objectives will be tested simultaneously, and include:
	Non-inferiority in each of 7 general mammographic features of the modified processing
CORE READING CENTER	The feature comparison study will be performed at International HealthCare, LLC in Norwalk, CT.
PRINCIPAL INVESTIGATOR	The principal investigator for this study is [name], MBA, FACR, FSBI.
AND READERS	The feature comparison study radiologist readers shall meet all criteria for their respective roles as specified in the investigational plan.
	The feature comparison study readers will participate in a training session to ensure their understanding of the ASPIRE Bellus II workstation, the protocol, the study CRFs, study processes, GCP, and their obligations as study participants.

# FEATURE COMPARISON STUDY DESIGN

Six MQSA-qualified and board-certified mammographers representing various experience levels, will be shown DBT images of a breast with the modified processing side-by-side the same breast with the original processing. One breast per subject (two views per breast; CC and MLO) will be evaluated by the readers. Readers will be blinded to the image reconstruction and presentation processing methods. Each reader will be given a different sample of cases to review. Approximately 600 total cases (100 cases per reader) will compose the sample. The order of the subjects and location (left or right review workstation high resolution monitor) of the images with modified processing will be randomized for each reader.

Readers will compare several general mammographic features. Readers will be asked to grade each feature on each view (CC and MLO) using the following 5-point scale, with specific training to use the score=0 category sparingly:

- -2 (left image much superior)
- -1 (left image somewhat superior)
- 0 (left and right images are equivalent)
- +1 (right image somewhat superior)
- +2 (right image much superior)

Interpretation instructions: The reader will complete the CRFs for each case for both CC and MLO views. The list of individual general mammographic features and lesion specific features are outlined below. Note that the results of the three lesion-specific features as well as diagnostic confidence (#8-11 below) will not be evaluated as part of this study.

- 1. Exposure, assessing visualization of the adipose and fibroglandular tissues and visualization of breast tissue underlying the pectoralis muscle, separately;
- 2. Breast composition, assessing overlapping breast structures, uniformity of exposure of fibroglandular tissues, adequacy of penetration of thicker portions of the breast, exposure of thinner areas and motion unsharpness;
- Image contrast for differentiation of subtle tissue density differences; permitting image contrast assessment adjustment of the window and level settings;
- 4. Sharpness, assessing the edges of fine linear structures, tissue borders, and benign calcifications;
- 5. Tissue visibility at the skin line;
- 6. Noise, i.e., noise obscuring breast structures or suggestive of structures not actually present:
- 7. Artifacts due to image processing, detector failure and other factors external to the breast on soft-copy displays; and
- 8. Ability to characterize a Mass (when present) based on conspicuity, margin sharpness, shape;
- 9. Ability to characterize Calcifications (when present) based on conspicuity, sharpness/shape, distribution;
- 10. Ability to characterize an Architectural Distortion (when present) based on conspicuity, sharpness.
- 11. Diagnostic confidence.

#### STUDY ANALYSIS

The proportion of cases where the readers judged the modified image processing as non-inferior will be calculated. Non-inferiority will be defined as a score of equivalence between modified and original or a score indicating the modified image processing is superior. For each reader, the proportion of cases judged as non-inferior with modified processing will be calculated for each feature and each view. A pooled estimate will also be calculated where the results over all readers and views will be combined. 95% percentile bootstrap CIs will be constructed for the pooled proportions of cases judged as non-inferior with the modified processing. These CIs will be reported for each feature.

The primary objective is the readers' assessment for each of the 7 general mammographic features. The null hypothesis is that the pooled proportion of cases judged as non-inferior with modified image processing is <0.50, versus the alternative hypothesis that the pooled proportion is >0.50. If the 95% CI does not contain values <0.50, then the null hypothesis will be rejected. These hypotheses will be evaluated for each of the 7 general mammographic features. If all 7 null hypotheses are rejected, then it will be concluded that the modified imaging features are non-inferior to the original imaging

May 15, 2018 Confidential Page 13 of 31 DOC-0038502-A

### 4. Fujifilm FMSU2013/2017 Applicable Series Protocols

### Fujifilm Protocol FMSU2013-004A

Acquisition of Digital Mammography and Breast Tomosynthesis Images for Clinical Evaluation of Fujifilm Digital Breast Tomosynthesis

### **Fujifilm Protocol FMSU2017-003**

A Feature Comparison Study to Evaluate the Modified Processing of Fujifilm's ASPIRE Cristalle with Digital Breast Tomosynthesis Option as Compared to the Original Processing

### 6. Background and Rationale

The following software changes have been made to the FDR-3000AWS of the PMA P160031 device; Dynamic Visualization II for mammography (DVIIm) and Iterative Super-Resolution Reconstruction (ISR).

DVIIm consists of EDR2 and MFP2, which are detailed as follows:

- Exposure Data Recognizer 2 for mammography (EDR2m) the EDR2m algorithm analyzes image data and identifies various anatomic structures using a statistical estimation method as opposed to original EDR's histogram analysis method. EDR2m determines the parameters to optimize brightness and contrast of the image based on the analysis result.
- Multi-Objective Frequency Processing 2 (MFP2) MFP2 optimizes the brightness, contrast and sharpness of the image using parameters determined by the EDR2m processing. MFP2 uses additional low frequency tables and a combination of automatic and preset dynamic range control operations.

Iterative Super-Resolution Reconstruction (**ISR**) is a new reconstruction algorithm that uses an iterative method to improve image quality including increased sharpness and lower noise. ISR applies super-resolution technology to improve the visibility of fine structures such as calcifications, and reduces the severity of artifacts.

**Note**: ISR replaces filtered back projection (**FBP**), and DVIIm (EDR2m and MFP2) replaces EDR and MFP, the methods used in the original PMA P160031 device.

#### 7. Investigational Plan

### 7.1. Purpose

The purpose of the feature comparison study is to evaluate general mammographic features of the same breast when reconstructed with modified (ISR and DVIIm) presentation processing as compared to the original processing (FBP with EDR and MFP).

### 7.2. Study Objectives

The primary objective is:

 Non-inferiority in each of the seven general mammographic features of the modified processing

### 7.3. Feature Comparison Study Population

Approximately 600 cases (breasts) will be selected from mammograms that were acquired under Fujifilm protocol FMSU2013-004A. Each of the six (6) readers will evaluate 100 unique cases in randomized order.

Table 1. Image Acquisition Sites and Principal Investigators

Image-Acquisition Site	Principal Investigator's Name	City, State
Elizabeth Wende Breast Care, LLC	[name]	Rochester, NY
Scottsdale Medical Imaging, LLC	[name]	Scottsdale, AZ
University of Iowa Hospitals and Clinics	[name]	Iowa City, IA
The University of North Carolina at Chapel Hill	[name], DO	Chapel Hill, NC
University of Texas San Antonio	[name]	San Antonio, TX

#### 7.3.1. Sample Size and Case Mix

Approximately 230 cancer cases and approximately 370 non-cancer cases will be selected by the statistician for this feature comparison reader study from the library of DBT mammograms collected under Fujifilm protocol FMSU2013-004A.

The approximately 370 non-cancer cases will include:

- approximately 190 biopsy benign cases,
- approximately 60 recall cases,
- approximately 60 normal cases, and

approximately 60 cases lost to follow-up.

#### 7.3.2. Inclusion and Exclusion Criteria

All cases for this feature comparison reader study will meet the following eligibility inclusion and exclusion criteria (see also Appendix B for complete inclusion and exclusion criteria from protocol FMSU2013-004A). Only subjects who were consented and met all inclusion criteria and none of the exclusion criteria were considered evaluable.

#### Inclusion Criteria

- Eligible subjects under protocol FMSU2013-004A, defined as female subjects with complete FFDM and DBT examinations, in which there is sufficient anatomical coverage, sufficient contrast, and no significant motion or other artifacts, as determined by the image-acquisition sites.
- Meet none of the exclusion criteria under protocol FMSU2013-004A.

#### **Exclusion Criteria**

- Subjects who are in violation of protocol FMSU2013-004A.
- Subjects who meet exclusion criteria under Fujifilm protocol FMSU2013-004A.

### 7.3.3. Case selection and Targeted Distribution

Cases will be randomly selected from Fujifilm's existing library (collected under protocol FMSU2013-004A). A stratified randomization is proposed where the strata and proposed sampling proportions are summarized in Table 2. Within each stratum, cases will be randomly selected so that approximately 10% have extremely dense breasts, 40% have heterogeneously dense breasts, 40% have scattered fibroglandular breasts, and 10% have fatty breasts.

Table 2. Sampling Plan

Stratum, defined by Reference Standard*	# available subjects	Overall sample composition	# cases per reader	Total # cases
Cancer: (N=229)				
Architectural Distortion	21		3-4	21
Microcalcification	86	38%	14-15	86
Asymmetry	19	30%	3-4	19
Mass	95		15-16	95
Other	8		1-2	8
Biopsy Benign: (N=457)				
Architectural Distortion	19		3-4	19
Microcalcification	212	32%	10	60
Asymmetry	43	3270	7-8	43
Mass	158		9	54
Other	25		2-3	15
Recalled/No Biopsy	98	10%	10	60
Negative	234	10%	10	60
Unknown	209	10%	10	60
Total	1227	100%	100	600

\*There are 1031 biopsied lesions in 894 subjects available for selection for this study. Because there are subjects with multiple lesions, cases in the table are organized first by the presence/absence of a malignant lesion, and then by presence/absence of an AD (and possibly another lesion), microcalcification, asymmetry, mass, and other, respectively. There were 208 subjects with lesions but no definitive biopsy diagnosis, including 24 ADs, 24 microcalcifications, 75 asymmetries, and 49 masses.

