### 8.4.4 Workflow for the Interpretation of Cases

Readers will be shown side-by-side images of the same breast reconstructed with the modified and original processing methods. One breast per subject (two views per breast) will be assessed by the readers. Readers will be blinded to the image reconstruction and processing methods. Each reader will be given a unique sample of cases to review. The order of the subjects and location (left or right review workstation high resolution monitor) of the images with modified processing will be randomized for each reader.

Within each stratum, cases will be randomly selected so that 10% have extremely dense breasts, 40% have heterogeneously dense breasts, 40% have scattered fibroglandular breasts, and 10% have fatty breasts.

Readers may interpret the preloaded cases in their assigned randomized order with the use of barcode scanner/barcodes.

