#### 9.3 Sample Size Justification

The following assumptions were made for determining sample size for the primary objectives:

- One breast per subject (two views)
- Each of six readers scores an independent sample of cases; thus, there is no correlation between readers' interpretations.
- 50% of cases have dense breasts
- >80% power is required

• 2.5% type I error rate (Note that hypothesis rejection depends on the lower bound of the 95% CI being greater than 0.50.)

Based on these assumptions, sample size was determined as follows:

$$M = \frac{\{1.96 \times \sqrt{0.5(1 - 0.5)} + 0.84\sqrt{p(1 - p)}\}^2}{[p - 0.5]^2}$$

where p is the proportion of comparisons judged as non-inferior under the alternative hypothesis. The sample size is given by N=M/(# readers). Table 4 summarizes the number of subjects needed per reader as a function of the proportion of cases judged as non-inferior with the modified processing.

Table 4. Number of Subjects Needed Per Reader for Tests of Non-inferiority

# readers	Proportion of Comparisons Judged as Non-inferior with Modified Processing (DVIIm plus ISR)				
	0.55	0.56	0.57	0.60	
6	131	91	67	33	

A study with 600 total subjects (i.e. 100 cases evaluated per reader) is proposed. This sample size would provide slightly more than 80% power to reject the primary null hypothesis, as long as  $\geq$ 56% of cases are judged non-inferior.

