where p is the proportion of comparisons judged as non-inferior under the alternative hypothesis. The sample size is given by N=M/(# readers). Table 1 summarizes the number of subjects needed per reader as a function of the proportion of cases judged as non-inferior with the modified processing.

#	Proportion of Comparisons Judged as Non-inferior with				
readers	Modified Processing (DVIIm plus ISR)				
	0.55	0.56	0.57	0.60	
6	131	91	67	33	

Table 1. Number of Sub	bjects Needed Per Reade	er for Tests of Non-inferiority
------------------------	-------------------------	---------------------------------

A study with 600 total subjects (i.e. 100 cases evaluated per reader) was proposed. This sample size would provide slightly more than 80% power to reject the primary null hypothesis, as long as \geq 56% of cases are judged non-inferior.

3. Randomization

Cases will be randomly selected from Fujifilm's existing library (collected under protocol FMSU2013-004A). A stratified randomization will be used where the strata and proposed sampling proportions are summarized in Table 2. Within each stratum, cases will be randomly selected so that approximately 10% would have extremely dense breasts, 40% would have heterogeneously dense breasts, 40% would have scattered fibroglandular breasts, and 10% would have fatty breasts.

Stratum, defined by Reference Standard*	# available subjects	Overall sample composition	# cases per reader	Total # cases
Cancer: (N=229) Architectural Distortion Microcalcification Asymmetry Mass Other	21 86 19 95 8	38%	3-4 14-15 3-4 15-16 1-2	21 86 19 95 8
Biopsy Benign: (N=457) Architectural Distortion Microcalcification Asymmetry Mass Other	19 212 43 158 25	32%	3-4 10 7-8 9 2-3	19 60 43 54 15

Table	2.	Sam	nling	Plan
IUDIC	_	Juin	PIIIS	I Iull

Recalled/No Biopsy	98	10%	10	60
Negative	234	10%	10	60
Unknown	209	10%	10	60
Total	1227	100%	100	600

Because there are subjects with multiple lesions, cases in the table were organized first by the presence/absence of a malignant lesion, and then by presence/absence of an AD (and possibly another lesion), microcalcification, asymmetry, mass, and other, respectively.

For each reader, a randomization list with 100 unique cases will be created consisting of four blocks:

- Block 1: 50 breasts from 50 subjects where the reader scored the CC view,
- Block 2: 50 breasts from a second sample of 50 subjects where the reader scored the MLO view,

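### Does taking every available cancer case defeat the plan's density mix in a way that calls for a change?

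*Protocol*

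**What the plan says.** Protocol 7.3.3 draws cases from the existing library: "A stratified randomization is proposed where the strata and proposed sampling proportions are summarized in Table 2". It then sets the density rule: "Within each stratum, cases will be randomly selected so that approximately 10% have extremely dense breasts, 40% have heterogeneously dense breasts", followed by 40% scattered fibroglandular and 10% fatty. SAP section 3 has the same rule: "Within each stratum, cases will be randomly selected so that approximately 10% would have extremely dense breasts". Protocol 8.4.4 repeats it without the softening word: "Within each stratum, cases will be randomly selected so that 10% have extremely dense breasts, 40% have heterogeneously dense breasts".

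The counts to be drawn are in Table 2, which is the same in both documents. Protocol 7.3.1 gives the overall case mix: "Approximately 230 cancer cases and approximately 370 non-cancer cases will be selected by the statistician". Protocol 8.4.4 fixes the unit: "One breast per subject (two views per breast) will be assessed by the readers". Protocol 9.3 and SAP section 2 list among the sample-size assumptions that "50% of cases have dense breasts".

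Neither document reports the density distribution of the library, says whether a stratum is one of the five reference-standard groups or one of the 13 rows, or says what happens to the density rule in a row where every subject is used.

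**The concern.** Selecting at random to a quota needs more subjects available than taken. Table 2 leaves no surplus in any cancer row, so on any reading of stratum the density rule has nothing to act on for the cancers. Choosing between a woman's two breasts does not restore a choice, because a cancer case is defined by the breast that holds the malignant lesion. Dropping cancers to meet the quota would break Table 2's own totals.

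If this mattered, three things could be at stake: a sample-size assumption (half the cases dense) that the selection does not secure; a pooled proportion averaged over a density mix other than the one described; and doubt over whether an off-target mix counts as a protocol deviation. Protocol 9.1 leaves the handling of deviations to the statistician.

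**Working it through.** **Inputs.** Table 2 (Protocol 7.3.3, SAP section 3), shown as taken/available:

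- Cancer: 21/21, 86/86, 19/19, 95/95, 8/8
- Biopsy benign: 19/19, 60/212, 43/43, 54/158, 15/25
- Recalled 60/98, negative 60/234, unknown 60/209

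**Table 2 totals.** Available: 229 + 457 + 98 + 234 + 209 = 1227. Taken: 229 + 191 + 60 + 60 + 60 = 600. Both match the table.

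**Cases with no selection step.**

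- Five-group reading: 21 + 86 + 19 + 95 + 8 = 229; 229/600 = 38.2%.
- Row reading: add benign architectural distortion and asymmetry, 19 + 43 = 62; 229 + 62 = 291; 291/600 = 48.5%. The other six rows fill 309 places from 936 subjects.

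The firm figure is 229. If biopsy benign is one stratum, its 191 - 62 = 129 selectable cases can offset the 62 fixed ones. With the 62 at a dense share x, the 129 would need to be (95.5 - 62x)/129 dense, which is 57.2% at x = 0.35 and 42.8% at x = 0.65.

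**Sample size.** The plan's formula is M = {1.96·√0.25 + 0.84·√(p(1-p))}² / (p - 0.5)², with N = M/6. At p = 0.55, 0.56, 0.57 and 0.60 it gives N = 130.3, 90.3, 66.3 and 32.3. Rounded up, these are 131, 91, 67 and 33, as in Protocol Table 4. No density term appears. Power with 600 cases at p = 0.56 is Φ((0.06·√600 - 1.96·0.5)/√(0.56·0.44)) = Φ(0.4897/0.4964) = 83.8%, consistent with the plan's claim of slightly more than 80%. Here p is the proportion pooled over whatever cases are read, so the density mix is already inside it.

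**Possible drift in the dense share.** Assume the fixed cases are 35% to 65% dense (not in the documents) and the rest are held at 50%.

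- Five groups: (229x + 371·0.5)/600 = 44.3% to 55.7%.
- Rows: (291x + 309·0.5)/600 = 42.7% to 57.3%.

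**Effect on the pooled proportion.** The shift equals the difference in non-inferior proportion between dense and non-dense breasts, times the departure of the dense share from 50%. Both differences below are assumptions.

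| Difference by density | Five groups | Rows |
|---|---|---|
| 10 points | 0.10 × 0.0573 = 0.6 points | 0.10 × 0.0728 = 0.7 points |
| 20 points | 0.20 × 0.0573 = 1.1 points | 0.20 × 0.0728 = 1.5 points |

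**Could half dense still be reached overall?** Yes, if the library allows. With cancers at dense share x, the 371 non-cancer cases would need to be (300 - 229x)/371 dense, which is 59.3% at x = 0.35 and 40.7% at x = 0.65.

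**The case for a change.** The strongest argument for a change is about conduct. Protocol 10.3 requires the study to be run as described, and one described step cannot be carried out for at least 38% of cases. Protocol 8.4.4 states the mix without qualification. Someone reading the results could believe that density was controlled among the cancers when it was not. The remedy would be cheap: a sentence on exhausted rows, a descriptive table, and perhaps density as a balancing factor across the six readers' lists.

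Part of this stands. Read literally, the rule has no effect among the cancers, and 8.4.4 is worded more firmly than 7.3.3 and SAP section 3. The rest does not carry it further. Table 2 is also part of what is described, and its counts settle what to do with the exhausted rows: take everyone. The section heading in 7.3.3 calls the distribution targeted, two of the three statements of the rule are approximate, and half dense is listed as an assumption. An exhausted row whose mix differs from the target says nothing against the validity of any single read, so it gives no ground for exclusion under 9.1. For balancing across readers, no imbalance is shown, and the analysis pools over readers with no density subgroup, weight or adjustment.

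**Conclusion.** No change is needed. The selection rule does not guarantee the 10/40/40/10 mix for 229 cases (38.2%), or for 291 (48.5%) if rows are strata. That is weaker than saying the mix will be missed: library density is not reported, so the cancers could already lie near the target, and the other 371 cases might compensate.

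Nothing that decides the trial depends on it. Sample size and power have no density term, the primary analysis is one pooled proportion per feature, and each case supplies its own comparison, so no bias between the two processing methods is shown. The sample is deliberately enriched (38% cancers), so its pooled proportion does not stand for a population density mix in any case. On the assumed ranges (fixed cases 35% to 65% dense, a 10- or 20-point difference by density), the pooled proportion moves by 0.6 to 1.5 points at most, in a direction the documents do not settle.

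Using every available cancer is a fair trade: the plan gets its 229 cancers and gives up control of their density. A statistician building the lists would take the exhausted rows as found and apply the target where there is surplus, which is also what reworded text would say.
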